As many HIV-infected children on ART survive to adulthood in sub-Saharan Africa, improving systems for disclosure and transition to adult care is a high priority. There is need for better data on transition in high volume HIV clinics in Africa, and these clinics require feasible, effective systematic approaches to improve disclosure and transition. A disclosure tool used in Namibia demonstrates effectiveness and acceptability and could be adapted for use in other settings. In addition, the Got Transition model, which was developed following broad expert consensus and programmatic evaluation in US settings, has a clear framework and useful resources relevant to pediatric HIV transition in Africa. Combining these interventions using an implementation science

approach (program evaluation, adaptation and a cluster RCT) has potential to provide high quality evidence for broader use of these approaches and to improve long-term outcomes for adolescents with HIV.

SECTION 2: OBJECTIVES

2a. Study Objective

This study aims to evaluate rates and co-factors of effective transition in HIV treatment programs in Kenya and to adapt, implement, and evaluate an Adolescent Transition Package (ATP) that combines an adapted US-based transition tool and a disclosure tool associated with improved disclosure outcomes in Namibia.

2b. Specific Objectives

Aim 1: To use programmatic data (KenyaEMR and paper files) to estimate prevalence of transition and disclosure, age at transition and disclosure, and individual-level co-factors of effective transition from pediatric to adult HIV care and retention and HIV disclosure among 10-24 year olds. To determine transition practices in Kenyan clinics using a facility survey.

Effective transition will be defined as enrollment into adult care within 6 months of exiting the pediatric care and continued clinical follow-up for at least 6 months thereafter, as evidenced by a second clinic visit recorded in the EMR.

Hypothesis: Transition will occur at varied ages (median 18 years); effective transition and earlier transition age will be associated with the presence of a transition plan and adolescent friendly services at the facility, later age at child HIV diagnosis, earlier age of HIV disclosure, parent on ART, better health status of the child at enrollment into HIV care and at transfer (CD4, WHO stage, viral load), pregnancy or marital status of the adolescent, and evidence of consistent adherence and retention prior to transition.

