An individual who meets any of the following criteria will be excluded from participation in this study: Conditions that would place the individual at increased risk or preclude the individual's full compliance with or completion of the study.

Table 4. Inclusion Criteria for all participants/clinics

	Population	Sampling	N	Inclusion Criteria
AIM 1: Program data abstraction				
Facility Survey Site	HIV care clinics	Selected randomly from clinics with EMR systems in place and >300 patients in HIV care	102	EMR system in place >300 patients in HIV care
Facility Survey Designee	HCW	Selected as representative for clinic to complete facility survey; will enroll 1-2 HCWs to help complete the survey per study site	102 sites	≥18 years of age Employed at facility in clinical care for at least 6 months and/or have a 1 year contract (i.e. not temporary staff) Provides clinical services to adolescents
Retrospective Records Review	Adolescents ages 10-24	All adolescents from the 102 selected facilities	Up to 15,000	-Aged 10-24 years of age -Attended clinic ≥1 time after January 1, 2016 -Attended clinic included in facility survey
Aim 2: ADAPT and OPTIMIZE				
Working Group	HCWs	Purposively selected from HCWs providing adolescent care	40 for Working Group	-≥18 years of age -Employed at clinic in Kenya -Employed in clinical care for at least 6 months and/or have a 1 year contract (i.e. not temporary staff) -Provides clinical services to adolescents
Adaptation IDI and FGDs	Adolescents (aged 14-24 years)	Adolescents in HIV care (8 FGDs for adolescents who have not completed transition, 8 FGDs for adolescents who have completed transition)	16 FGDs and 96 adolescents total (from clinics with different models of care)	-Ages 14-24 -Seeking treatment services at facilities assessed in Aim 1 -Knows that they have HIV -Attended clinic for at least 1 year
	Caregivers of HIV-infected adolescents aged 14-24 years	Caregivers of adolescents who have and have not completed transition	8 FGDs and 48 caregivers total (from clinics with different models of care)	-≥18 years of age -Seeking treatment services at facilities assessed in Aim 1 -Caregiver of adolescent age 14-24 years seeking treatment at selected site -Adolescent has attended clinics for at least 1 year

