For each clinic that agrees to participate, routine clinic data will be abstracted from the EMR system and from paper forms when EMR systems are not available. The medical records collected from the patient charts will include data tracking routine services offered and laboratory measurements collected. EMR or other medical record data will be abstracted directly from clinics or from implementing partners, whichever is most convenient for the clinic. If data staff at the partner organization or at the clinic are unable to extract the data on their own, hired technicians or study staff will travel to sites and assist with data abstraction directly. All medical records for adolescents ages 10-24 attending the clinic at least 1 time between January 1, 2016 and the date of data abstraction (but not later than December 31, 2017) will be pulled.

Data Collection Procedures:

For EMR data, data will be extracted by running a standardized query of the EMR database. The query will pull serial records for all adolescents ages 10-24 years who have at least 1 visit on or following January 1, 2016 and attend a clinic selected to participate in the facility survey. This will include all data on each adolescent from January 1, 2016 up until the date when data is abstracted but not later than December 31, 2017. We will not obtain individual consent for pulling adolescent records from the EMR. We will obtain a waiver of consent to obtain this information. Data collected will obtain basic demographic and HIV-specific clinical care outcomes as detailed in the attached file listing variables to be collected. This information is already charted as part of routine care. For paper records, data will be abstracted using Case

Report Forms (CRFs) and Open Data Kit (ODK) or REDCap. We will abstract selected variables from the EMR and paper based records including: client age at enrollment, caregiver type, sex, date/age of HIV diagnosis, CD4 count or percent, date of ART initiation, attendance at pediatric or adult clinic day (data obtained from facility survey and calculated by visit dates), and presence of caregiver at the visit (in EMR counseling notes). Serial data will be obtained on follow-up at the clinic. A list of variables that will be collected is attached.

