A total of up to 60 providers will be selected from among all providers at intervention facilities, including 10 IDIs with ATTACH study staff. HCWs will be purposively selected to represent different cadres of HCWs who provide services for adolescents and are directly involved in implementation of the ATP. We believe that 5 providers per site (50 total), and 10 ATTACH study nurses, will give us adequate numbers to attain saturation during data collection and enough diversity in health provider cadre to ensure different perspectives are accurately represented.

A total of up to 96 adolescents will be selected for interviews. We will purposively select adolescents with a range of ages and intervention exposure. Clinic providers will assist in identifying and referring adolescents who are aware of their HIV status and have been through disclosure as well as adolescents who have been exposed to the ATP. Eligibility of adolescents will be confirmed by reviewing their chart for documentation of disclosure and transition intervention exposure. We believe that 6-10 adolescents from each site (96 total) will give us adequate numbers to attain saturation during data collection and will provide enough diversity in experiences to ensure different perspectives are accurately represented.

11b. Overview of analysis plan

Aim 1

Follow-up at 6-month post-enrollment and annually thereafter will be determined and summarized as proportion retained for given interval (e.g., 6-month retention, 12-month retention, 36-month retention) with anticipated denominator in follow-up based on enrollment date. Cofactors for loss to follow-up will be determined using Cox regression. Potential cofactors of loss to follow-up include age at enrollment, CD4, caregiver type (biologic, mother or father), age at HIV diagnosis, sex, illness or hospitalization, and evidence of transition. Proportion with evidence of transition and mean/median age of transition will be computed. Cofactors of transition will be determined including child/adolescent age, age at HIV diagnosis, evidence of disclosure, caregiver type using logistic regression. Post-transition retention will be determined and cofactors of effective transition (documented 6-month or longer follow-up after transition) will be assessed using logistic regression.

Aim 2

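### Aim 1 fits a yes/no logistic model for transition to unequally observed records, which biases cofactors tied to short observation among youth still in pediatric care

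*Combined protocol and SAP*

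**What the plan says.** Protocol Section 11b, Aim 1, plans the proportion with evidence of transition and the mean or median age at transition, and then: "Cofactors of transition will be determined including child/adolescent age, age at HIV diagnosis, evidence of disclosure, caregiver type using logistic regression". Effective transition is modelled in the same way: "cofactors of effective transition (documented 6-month or longer follow-up after transition) will be assessed using logistic regression". For loss to follow-up the same paragraph takes a different route: "Cofactors for loss to follow-up will be determined using Cox regression". Retention there also has a denominator set by enrolment date.

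Entry needs a single visit. Table 4 has "Attended clinic ≥1 time after January 1, 2016", and Section 7a has "All medical records for adolescents ages 10-24 attending the clinic at least 1 time between January 1, 2016 and the date of data abstraction". Section 7a caps every clinic's data at 31 December 2017, so the window is at most 24 months.

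For transition, Section 11b states no risk set, minimum follow-up, fixed horizon, follow-up offset or censoring rule. The SAP deals only with the cluster trial and adds nothing on Aim 1.

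**The concern.** A youth who is in pediatric care and seen for two months has had little time to be recorded as transitioned. A logistic model gives that record the same weight as a non-transition over two years. A factor that shortens observation then looks like a barrier to transition even if it has no effect.

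The protocol itself gives reason to expect observation time to differ by cofactor. Its list for loss to follow-up reads "Potential cofactors of loss to follow-up include age at enrollment, CD4, caregiver type (biologic, mother or father), age at HIV diagnosis, sex", and age, caregiver type and age at HIV diagnosis are also named as cofactors of transition. Section 1b reports twofold higher loss at 15-24 years than in younger adolescents. Section 2b hypothesises that "later age at child HIV diagnosis" and good retention before transition go with effective and earlier transition. If later-diagnosed youth enrolled more recently, the first is biased downwards. The second is tied directly to time observed.

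At stake is the reading of the Aim 1 cofactor results. No cluster-trial endpoint depends on this model.

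**Working it through.** **1. The plan's own Aim 1 figure.** Section 11a uses prevalence 60%, precision 2.5%, ICC 0.05 and 50 youth per clinic. The simple-random-sample size is 1.96² × 0.6 × 0.4 / 0.025² = 1475.1. The design effect is 1 + 49 × 0.05 = 3.45. Then 1475.1 × 3.45 / 50 = 101.8, or 102 clinics, as stated. That figure concerns prevalence precision and has no bearing on the transition model.

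**2. Inputs for the bias.**
- Transition rate: 20% in 2 years, which is the Aim 3 control-arm assumption in Section 11a. The documents give none for Aim 1.
- Hazard: assumed constant, h = −ln(0.8)/2 = 0.1116 per year.
- 24-month loss: 20% and 25% (control-arm values in Table 8), with 10% as a lower value.
- True effect of the factor: none.
- Population: youth in pediatric care at first visit.

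**3. Loss to follow-up.** With loss hazard m and window T = 2 years, P(transition recorded) = h/(h+m) × [1 − exp(−(h+m)T)]. Doubling m in one group gives:

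| Reference 24-month loss | P, doubled loss | P, reference | Odds ratio |
|---|---|---|---|
| 10% | 0.181 | 0.190 | 0.94 |
| 20% | 0.163 | 0.180 | 0.88 |
| 25% | 0.154 | 0.175 | 0.86 |

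**4. Staggered entry.** For a group entering evenly over the window, P = 1 − (1 − exp(−2h))/(2h) = 1 − 0.2/0.2231 = 0.104. Against 0.200 for a group seen for 24 months, the odds ratio is (0.104/0.896)/(0.200/0.800) = 0.46.

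**5. Dilution by youth already transitioned.** Section 11a assumes, for Aim 3, that 20% of those aged 15-24 are in a pediatric program. Suppose the other 80% all count as transitioned at entry. The entry contrast becomes 0.8 + 0.2 × 0.104 = 0.821 against 0.8 + 0.2 × 0.200 = 0.840. The odds ratio is then (0.821/0.179)/(0.840/0.160) = 0.87.

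**6. Does a time-based model remove it?** This was checked in 60 simulated datasets per scenario, each with 5000 youth, one binary factor splitting them about equally, no true effect and no clustering.

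| Scenario | Logistic odds ratio | Logistic p<0.05 | Person-time rate ratio | Person-time p<0.05 |
|---|---|---|---|---|
| Doubled loss, reference 20% | 0.87 | 42% | 0.99 | 2% |
| Uniform entry, no loss | 0.47 | 100% | 1.01 | 0% |
| Both | 0.45 | 100% | 1.00 | 7% |

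Loss in these simulations is unrelated to transition, so they show that unequal time is corrected. They do not show that censoring at loss is safe in the real data.

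**The case against.** **Prevalence is a legitimate target.** Section 3 lists prevalence of transition as an Aim 1 outcome. For status in the record, a proportion and a logistic model are conventional, and a youth seen once on an adult day can carry evidence of transition. This stands: the descriptive proportion should stay, and the bias belongs to incident transitions among youth who start the window in pediatric care. The plan does not separate the two groups.

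**The plan does not say how brief records are coded.** True. Not transitioned is the default of a yes/no model, and no other rule is given. The cofactor list is open, so follow-up time could be added, but the plan does not say that it will be.

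**Observation may vary less than 0 to 24 months.** Section 5b describes youth currently engaged in care, Section 11a refers to enrolment in care over the previous 12-24 months, and Section 11b mentions 36-month retention. These sit uneasily with the entry rule, but none sets a minimum follow-up for the transition model.

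**The large odds ratios are the extreme end.** This stands. A reader might infer that age at diagnosis will show a marked false effect. If 50% of later-diagnosed and 10% of earlier-diagnosed youth entered during the window, the null odds ratio would be 0.76 (0.152 v 0.190). That split is not in the documents, and the figure is 0.95 (0.830 v 0.838) if 80% already count as transitioned. A constant hazard is also crude when Section 2b expects a median transition age of 18 years.

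**Clinic abstraction dates.** A reader might infer that facility comparisons are badly distorted by differing abstraction dates. The documents do not support this: Table 6a places extraction in one quarter (Figure 6b is broader), and all clinics share the same cap.

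**Simple censoring has its own fault.** Youth who leave pediatric care and never reach adult care are the failures that Aim 1 studies. Censoring them as non-informative could hide failed transitions. This stands and shapes the fix.

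**Conclusion.** The concern holds for cofactors of transition among youth in pediatric care at their first in-window visit. For them the model as written confuses not transitioning with not being observed for long, and the error runs towards odds ratios below 1 for factors linked to recent enrolment or early loss.

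The size cannot be fixed from the documents. Under the borrowed 20% rate and constant hazard, it is modest through loss to follow-up (0.86 to 0.94) and large for uniform entry against full observation (0.46). Mixing in many youth already transitioned brings the latter to about 0.87. Effects of abstraction date are likely small.

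The documents do not support saying that the prevalence estimate is invalid, that any named cofactor will come out reversed, or that the trial's results are affected. The same structure applies to effective transition, which also needs at least 6 months of later follow-up; that was not sized here. The change is worth making because the same paragraph already uses a time-to-event method for loss to follow-up in these records.

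**What to change.** In Section 11b, Aim 1:

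- Keep the proportion with evidence of transition as the descriptive prevalence outcome, and state its denominator.
- For cofactors of transition, restrict to youth in pediatric care at their first in-window visit and replace the logistic model by a time-to-event model. Use age as the time scale with delayed entry at that visit, the dated transition as the event, and the clinic's abstraction date as the end of observation.
- Treat loss from care or death as a competing event, or examine it in a sensitivity analysis, rather than simply censoring it as non-informative. State how loss is dated.
- Add the cumulative incidence of transition by 12 and 24 months.

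No new data are needed. Section 7a already pulls dates of birth, serial visits and pediatric or adult clinic day by visit date, and age at transition is already to be reported. The cost is protocol wording and a little more analysis work, including a rule for being in pediatric care at clinics without separate days. The downside is that results become hazard ratios and describe incident transitions only.

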- *Prospective Data - Demographic information:* We will collect demographic information for all participating in the FGD/IDIs. Demographic surveys for each population included in IDIs or FGDs are attached as appendices.
- *Retrospective and Prospective Data - Clinic records:* Adolescent clinic records from the EMR system and routinely collected paper forms will be extracted from all clinics participating in Aim 1 and at baseline, and throughout the RCT, for clinics participating in Aim 3 to assess clinical adolescent outcomes. Data from each pull will capture all records until the previous data pull (Aim 3) or from between January 1, 2016 and December 31, 2017 (Aim 1). Examples of data will be enrollment age, CD4, viral load (where available), WHO stage, hospitalization, caregiver presence, serial visits since enrollment, pediatric or adult clinic day of attendance and reported adherence. This will be collected from the clinic medical records database or paper clinic records, a clinic partner organization, or other location where medical record data for selected clinics is being stored and managed such as the Kenyan National Data Warehouse.
- *Prospective Data - Disclosure checklist:* This will be completed at every clinic visit to obtain more detailed data on partial and full disclosure in both intervention and control sites. This data will be abstracted from patient files routinely throughout the RCT.
- *Prospective Data - Transition booklet tracking form:* This will be completed at every clinic visit to obtain more detailed data on transition in intervention sites. This data will be abstracted from patient files routinely throughout the RCT.
- *Prospective Data - Transition tracking log:* This will be completed at transition to adult clinics and for next 6 months for both intervention and control sites. This data will be abstracted from patient files routinely throughout the RCT. .
- *Prospective Data - Pre-Trial surveys:* Surveys will be conducted with adolescents who have completed disclosure or transitioned to adult care and HCWs from intervention sites. Adolescent surveys will be conducted for both intervention and control sites at the beginning of the study. Information will include basic demographics (age, schooling) and satisfaction with services received. HCW surveys include basic demographic information, initial impressions of the ATP, and implementation climate.

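### Aim 1 counts a transition as effective only with 6 months of documented follow-up but sets no minimum potential follow-up, so transitions in the last 6 months before abstraction cannot qualify

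*Combined protocol and SAP*

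**What the plan says.** Section 2b (Aim 1) defines effective transition in two parts. The first is "enrollment into adult care within 6 months of exiting the pediatric care". The second is "continued clinical follow-up for at least 6 months thereafter, as evidenced by a second clinic visit recorded in the EMR".

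Section 11b (Aim 1) turns this into a binary outcome: "cofactors of effective transition (documented 6-month or longer follow-up after transition) will be assessed using logistic regression".

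Section 7a limits the EMR query to "all data on each adolescent from January 1, 2016 up until the date when data is abstracted but not later than December 31, 2017". Section 10 gives the same two dates for the Aim 1 clinic records.

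The same paragraph of section 11b does allow for limited observation time in two other outcomes. Retention is reported "with anticipated denominator in follow-up based on enrollment date", and loss to follow-up is analysed by Cox regression. Neither provision is extended to effective transition. The analysis plan finalised in February 2020 covers only the cluster trial and adds nothing for Aim 1.

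**The concern.** The outcome needs a fixed stretch of time after the transition, but the records stop on a fixed date. A young person who entered adult care in October 2017 and stayed in care cannot show 6 months by the end of December 2017. With a yes/no outcome and no rule to exclude or censor such cases, the natural coding of an undocumented follow-up is not effective.

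Two results are at stake. The estimated proportion with effective transition would be too low. The cofactor odds ratios would also be distorted, because part of what the model calls failure is only lack of time. Section 2a makes rates and cofactors of effective transition part of the study objective, and section 3 lists individual-level and facility-level cofactors of it as Aim 1 outcomes. Facility-level cofactors are the most exposed, because the closing date can differ from clinic to clinic.

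**Working it through.** **The plan's own Aim 1 figure.** Section 11a uses a prevalence of 60%, precision of 2.5 points, 95% confidence, ICC 0.05 and 50 adolescents per clinic.
- Simple random sample: 1.96² × 0.6 × 0.4 / 0.025² = 1475.1.
- Design effect: 1 + 49 × 0.05 = 3.45.
- Clinics: 1475.1 × 3.45 / 50 = 101.8, rounded up to 102.

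This reproduces the stated 102. It concerns retention and viral suppression and is not in question.

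**Length of the window.** 1 January 2016 to 31 December 2017 is 731 days, or 24.0 months, at most. The last 6 months, 1 July to 31 December 2017, are 184 days: 184/731 = 25.2%. Earlier abstraction shortens the window.

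**Share of transitions that cannot qualify.** Assume transitions are uniform over a window of W months. The share with less than 6 months left is 6/W. If these are coded as not effective, observed proportion = true proportion × (1 − 6/W). The true values below are illustrative; the documents give none for Aim 1.

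| W (months) | 6/W | True 50% appears as | True 70% | True 80% | True 90% |
|---|---|---|---|---|---|
| 24 | 25% | 37.5% | 52.5% | 60% | 67.5% |
| 18 | 33% | 33.3% | 46.7% | 53.3% | 60% |
| 12 | 50% | 25% | 35% | 40% | 45% |

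**Effect on cofactors, W = 24.**
- *Same timing in both groups.* True 60% v 40% has an odds ratio of (0.60/0.40)/(0.40/0.60) = 2.25. The observed proportions are 45% and 30%, so the odds ratio appears as (0.45/0.55)/(0.30/0.70) = 1.91. True 80% v 60% (odds ratio 2.67) becomes 60% v 45% and appears as 1.83.
- *Different timing.* Take a true 70% in both groups, with 35% of one group and 15% of the other transitioning too late. The observed proportions are 0.70 × 0.65 = 45.5% and 0.70 × 0.85 = 59.5%. The odds ratio is (0.455/0.545)/(0.595/0.405) = 0.57, where the truth is 1.

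**Dependence on the denominator.** Section 2b allows up to 6 months between pediatric exit and adult entry. Suppose exits are uniform over 24 months and the delay is uniform over 0 to 6 months, with a mean of 3.
- Adult entry falls inside the window for (24 − 3)/24 = 21/24 of exits.
- Adult entry plus 6 months falls inside it for (18 − 3)/24 = 15/24.
- Loss among documented transitions: 1 − 15/21 = 28.6%.
- Loss among all exits: 1 − 15/24 = 37.5%.

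**The case against.** The strongest reply is that the plan never says how a late transition is coded. Section 11b is an overview, and its retention rule shows that the authors do restrict denominators by available time, so an analyst might well do the same here. It is true that the coding is an inference: a reader might take the plan to state that late transitions are failures, and it does not. But the outcome is binary, the 6 months must be documented, and the retention and Cox provisions are confined to other outcomes. Applied literally, the rule leaves a late transition no way to succeed.

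A second reply is that section 2b accepts a second clinic visit as evidence, and section 7b puts visits at about every 3 months. If one routine visit were enough, the affected share would fall to about 3/24 = 12.5%. However, section 2b still asks for at least 6 months, and section 11b says 6 months or longer.

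Third, section 3 lists the prevalence of transition, not of effective transition, among the Aim 1 outcomes. That is correct, so a reader should not call the proportion effective a headline listed outcome. Its standing comes from the objective in section 2a and from the listed cofactor analyses.

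Finally, none of the cofactors named in section 11b is calendar time or abstraction date. Without a link between a cofactor and timing, the result is attenuation only. That stands.

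**Conclusion.** The point holds. As written, transitions in the last 6 months before a clinic's abstraction date cannot be effective. Under uniform timing this is about 25% of transitions with the full 24-month window, 33% at 18 months and 50% at 12. The proportion effective is lowered by the same fraction, and associations are pulled towards the null. False associations are possible, but only where a cofactor is related to transition timing or abstraction date; the documents do not show that any is.

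Two stronger figures are tempting. A reader might put the loss at 37.5%, but that needs all pediatric exits as the denominator. Section 11b measures follow-up after transition, and among documented transitions the same assumptions give 28.6%. A reader might also apply the loss to a true value of 60%, but in section 11a that figure belongs to retention and viral suppression.

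The sizes rest on uniform timing and on late cases being coded as not effective. The effect is confined to Aim 1: the Aim 3 analysis is untouched.

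**What to change.** Add a rule to section 11b (Aim 1) that names the denominator and the potential follow-up it requires:
- If the denominator is documented transitions, include only adolescents whose adult-care entry was at least 6 months before their clinic's abstraction date (about 30 June 2017 at the latest).
- If it is all pediatric exits, as the section 2b definition implies, include only exits at least 12 months before that date (31 December 2016 at the latest). This gives everyone the full entry gap plus 6 months, including those who never enter adult care.
- Alternatively, analyse time from adult-care entry to loss to follow-up, censored at abstraction, and report 6-month retention. The clock should start at adult-care entry. Timed from pediatric exit, someone who enters at month 5 and is lost at month 7 would pass at 6 months yet fail section 2b.

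The same sentence should say which visit proves 6 months of follow-up.

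No new data are needed. Under uniform timing over 24 months, the 6-month rule drops about 6/24 = 25% of transitions and the 12-month rule about 12/24 = 50% of exits. Shorter windows cost more: at 18 months, 33% and 67%. The censored analysis keeps the late transitions, but it covers only those who entered adult care.
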